6.7.11. Correlation Analysis on Reduction in uPCR and Change in eGFR

An exploratory correlation analysis exploring the relationship between the reduction in uPCR and change in eGFR will be considered at week 26, with correlation coefficients provided. The analysis may be repeated based on alternative populations (such as ITT or subgroups based on baseline level) or uPCR reduction metrics (such as change from baseline, percentage change from baseline, or absolute levels) if needed.

7. SAFETY ANALYSIS

The safety analysis will be performed using the Safety Set. Safety variables include AEs, clinical laboratory data, vital signs, and ECGs. For each safety variable, the last value collected before the first dose of the investigational product will be used as a baseline for all analyses of that safety variable.

All safety analyses will be conducted according to the treatment the participant actually received.

7.1. Adverse Events

Treatment-emergent adverse events (TEAEs) are defined as those AEs that develop or worsen after the first dose of double-blinded investigational product and up to 56 days beyond the last dose of investigational product. Analysis of AEs (as discussed below) will be limited to TEAEs, but data listings will include all AEs regardless of their timing.

All reported AEs will be coded using the current version of MedDRA and summarized by System Organ Class (SOC) and Preferred Term (PT). All summaries by SOC and PT will be ordered by decreasing frequency of participants within each SOC and then similarly by decreasing frequency of participants within each PT based on the pegcetacoplan group. In the case of equal frequency of number of participants in SOCs or PTs, summaries of TEAEs will be sorted alphabetically. Rules for handling missing severity, relationship to study drug, relationship to infusion procedure, outcome, and missing dates of AEs are described in Section 13.

If a PT was reported more than once for the same participant, that participant would only be counted once in the incidence for that PT. For participants experiencing the same PT at multiple severities, the occurrence of the AEs with the greatest severity will be used in the analysis of incidence by severity. For participants experiencing the same PT at multiple relationship levels, the occurrence of the AEs with the strongest relationship to study drug will be used in the analysis of incidence by relationship to study drug.

The AE summaries will be presented by treatment group. In addition, the incidence of death, stratified by transplant history will be summarized.

In post-transplant participants, the number and incidence of rejection episodes at week 26 will be tabulated by treatment group. Additionally, if the number of participants is sufficient, the results for treatment groups will be compared using Fisher's exact test (or a stratified Cochran-Mantel-Haenszel χ -square test as appropriate).

In participants who are posttransplant, the number and incidence of graft loss at week 26 will be tabulated by treatment group. Additionally, if the number of participants is sufficient, the results for treatment groups will be compared using Fisher's exact test (or a stratified Cochran-Mantel-Haenszel γ -square test as appropriate).

An overall summary for TEAEs, including number of participants who experience a TEAE, number of total TEAEs, and number of unique TEAEs, will be provided:

- TEAE
- Treatment-related TEAE
- Infusion-related TEAEs
- Serious TEAE
- Maximum severity of TEAEs
- Infusion site reaction
- TEAE leading to treatment withdrawn
- TEAE leading to dose interruption
- TEAE leading to study discontinuation
- TEAE leading to death
- Rejection episodes (for posttransplant only, based on PTs of "KIDNEY TRANSPLANT REJECTION", "RENAL AND PANCREAS TRANSPLANT REJECTION", "MULTIPLE ORGAN TRANSPLANT REJECTION", "SOLID ORGAN TRANSPLANT REJECTION")
- Graft loss (for posttransplant only, based on PTs of "TRANSPLANT FAILURE",
 "ENGRAFT FAILURE", "RENAL TRANSPLANT FAILURE", "REMOVAL OF
 RENAL TRANSPLANT", "GRAFT LOSS")

The following summaries will be provided:

- TEAEs by SOC and PT
- TEAEs by PT in decreasing order of frequency
- Treatment-related TEAEs by SOC and PT
- Infusion-related TEAEs by SOC and PT
- Serious TEAEs by SOC and PT
- TEAE by SOC, PT and maximum severity
- TEAE leading to treatment discontinuation by SOC and PT
- TEAE leading to dose interruption by SOC and PT
- TEAE leading to study discontinuation by SOC and PT
- TEAE leading to death by SOC and PT
- Treatment-emergent adverse events of special interest (AESIs) by SOC and PT
- Serious treatment-emergent AESIs by SOC and PT
- Exposure-adjusted incidence TEAEs by SOC and PT
- Exposure-adjusted incidence serious TEAEs by SOC and PT

Exposure-adjusted incidence rate of an AE is defined as the number of events divided by the total duration of exposure of the participants at risk during treatment, which is computed as following:

Exposure-adjusted incidence rate = n*100/EY,

where n is the number of participants impacted; the exposure year (EY) = (sum of time to onset of the event)/365.25, where time to onset of the event = date of onset of event – Day 1 date +1. For participants without the event, time to onset is censored as follows: time to onset of the event = (last dose date + 56 days) – Day 1 date +1. For participants who experienced the same event on multiple occasions: time to onset of the event = date of onset at the first occasion – Day 1 date +1.

The following listings will be provided:

- All AEs
- Serious adverse events (SAEs)
- AEs leading to study drug discontinuation
- Death
- Treatment-related adverse events
- Infusion-related adverse events

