12.4. Safety Analysis

All safety analyses will be summarized for the safety set.

AEs will be coded using the current version of the Medical Dictionary for Regulatory Activities at the time of analysis. TEAEs will be summarized by System Organ Class, Preferred Term, and treatment group for the number of participants and proportion reporting the event. A similar summary will be produced for SAEs, AEs leading to discontinuation of study drug, severe AEs, and AEs related to the investigational product.

The intensity of AEs and the relationship to investigational product will be summarized for each System Organ Class and Preferred Term by treatment group.

Withdrawals due to AEs will be summarized for each body system and Preferred Term by treatment group.

The AE summaries will be presented across all participants. All AEs will be listed by participant along with information regarding onset, duration, relationship to study drug, severity, action taken with study drug, treatment of event, and outcome. In addition, the number and incidence of rejection episodes and graft loss as well as the incidence of death stratified by transplant history will be tabulated.

In participants who are post transplant, the number and incidence of rejection episodes at week 26, will be tabulated by treatment group and compared between treatment groups using Fisher's exact test or a stratified Cochran-Mantel-Haenszel χ -square test as appropriate. The number and incidence of rejection episodes at week 52 will be tabulated.

In participants who are post transplant, the number and incidence of graft loss at week 26 will be tabulated by treatment group, and the results for treatment groups will be compared using Fisher's exact test or a stratified Cochran-Mantel-Haenszel χ -square test as appropriate. The number and incidence of graft loss at week 52 will be tabulated.

Changes from baseline in clinical laboratory test results will be summarized, using descriptive statistics, by visit and nominal time postdose. Baseline will be taken as the measurement closest to but before randomization. Out-of-range values will be flagged in data listings.

ADA results, ECG results, and changes from baseline in vital sign measurements will be summarized by treatment group, using appropriate descriptive statistics. Baseline will be taken as the measurement closest to but before randomization.

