2.2.5. Safety Endpoints

The safety endpoints are as follows:

- The incidence and severity of treatment-emergent adverse events (TEAEs)
- The change from baseline in:
 - vital signs measurements
 - clinical laboratory tests
 - Electrocardiogram (ECG) results
- The number and incidence of rejection episodes (posttransplant participants only)
- The number and incidence of graft loss (posttransplant participants only)
- The incidence of death, stratified by transplant history

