5.5. Prior and Concomitant Procedures

Prior and concomitant procedures will be coded using the latest MedDRA version available. Summaries of prior and concomitant procedures will be presented by SOC and PT with numbers and percentages by treatment groups and overall for participants in the Safety Set. Prior procedures are defined as those that started prior to the first administration of study drug. Concomitant procedures are defined as those that started on/after the date of first administration of study drug. Procedures that started before the first dose of study drug and continuing after will be considered as both prior and concomitant procedures. A data listing of all procedures will be provided for the Safety Set.

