6.3. Estimands

The primary objective of this study is to assess the efficacy of twice-weekly SC doses of pegcetacoplan compared with that of placebo in patients with primary C3G or IC-MPGN on the basis of a reduction in proteinuria.

The estimands and their attributes for the primary and all comparative key secondary and additional secondary endpoints are shown in Table 1 below. This includes strategies for addressing the following intercurrent events (ICEs):

- ProhibiRescue = use of prohibited concomitant medication specified in Protocol Section 8.3.3, or use of rescue therapies defined in Protocol Section 8.3.2
- RenalReplace = start renal replacement therapy (dialysis and/or renal transplant)
- DisctTrt = permanent discontinuation of study treatment

Table 1: Estimands and Attributes for Primary, Key Secondary, and Additional Secondary Endpoints

Socona	Secondary Endpoints				
For all estimands: A. Population: participants with C3G or IC-MPGN defined through the study inclusion/exclusion criteria in the ITT Set B. Treatment regimens of interest: • Twice-weekly SC doses of pegcetacoplan for 26 weeks of treatment • Twice-weekly SC doses of placebo for 26 weeks of treatment					
C: Variable (or endpoint) D: Strategies for addressing ICEs (event†: strategy‡) E: Population-level sum					
Primary Estimand					
Log-transformed ratio of uPCR at week 26 compared to baseline	ProhibiRescue: hypothetical strategy RenalReplace: hypothetical strategy DisctTrt: treatment policy strategy	Difference in mean change of log-transformed uPCR from baseline to week 26 (measured by equal-weighted average over weeks 24, 25, and 26) between the pegcetacoplan group and the placebo group.			
Key Secondary Estimands	(for comparative endpoints)				
The proportion of participants who meet the criteria for achieving a composite renal endpoint at week 26	ProhibiRescue, RenalReplace, DisctTrt: composite strategy	Odds ratio of achieving a composite renal endpoint for the pegcetacoplan group to achieving a composite renal endpoint for the placebo group at week 26.			
The proportion of participants with a reduction of at least 50% from baseline in uPCR at week 26	ProhibiRescue, RenalReplace, DisctTrt: composite strategy	Odds ratio of achieving a reduction of at least 50% from baseline in uPCR for the pegcetacoplan group to achieving a reduction of at least 50% from baseline in uPCR for the placebo group at week 26.			

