7. SAFETY ANALYSIS

7.1. Adverse Events

Further detail is provided in the main SAP Section 7.1. The same summaries for RCP as in the main SAP will be repeated for OLP (except for rejection episodes and graft loss where only descriptive summaries are required at Week 52) using all available data through the Week 52 assessment.

Besides the AESI summaries as per the CRF form checkbox question "Is this event an AESI?", additional summaries for the AEs of special search will be provided based on the special search teams provided by Apellis safety team, more specifically:

- Infections: SOC-infections and infestations; HLGT- Bacterial infectious disorders, HLGT- Fungal infectious disorders, HLGT- Viral infectious disorders
- Hypersensitivity: SMQ-Hypersensitivity (narrow)
- Acute Kidney Injury: SMQ- Acute Renal Failure (narrow)
- Thrombocytopenia: HLT- Thrombocytopenias, PT-Platelet count decreased, PT-Plateletcrit decreased, PT-Platelet count abnormal

AEs will be summarized by treatment groups and period. Data will be presented in 5 columns: (1) Pegcetacoplan group's RCP results; (2) Pegcetacoplan group's OLP results; (3) Placebo group's OLP results; (4) OLP results combined (in other words, combining columns 2 and 3); (5) for all results since Pegcetacoplan injection (in other words, combining columns 1 and 4). The classification of AEs in the RCP or OLP will be based on the AE start date compared to the RCP/OLP threshold as defined in the main SAP Section 13.3.

For AE summaries that relate to rejection episodes, in addition to the preferred terms specified in the main SAP, one additional preferred term of "Transplant rejection" is also added based on Apellis team review.

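### Graft loss is identified only from five treatment-emergent preferred terms, so a transplant recipient who starts permanent dialysis or is re-transplanted may be missing from the graft-loss count

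*SAP*

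**What the plan says.** SAP 2.2.5 lists the endpoint as "The number and incidence of graft loss (posttransplant participants only"), and Protocol 5.2.2 names it too. Protocol 12.4 sets out the week 26 table and a between-arm test but gives no case definition: "In participants who are post transplant, the number and incidence of graft loss at week 26 will be tabulated by treatment group, and the results" are to be compared by Fisher's exact test or a stratified Cochran-Mantel-Haenszel test.

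SAP 7.1 repeats the table: "In participants who are posttransplant, the number and incidence of graft loss at week 26 will be tabulated by treatment group", with a test only if numbers suffice. Among the items of the overall TEAE summary, the same section has "Graft loss (for posttransplant only, based on PTs of" five terms: transplant failure, engraft failure, renal transplant failure, removal of renal transplant, and graft loss. It also restricts scope: "Analysis of AEs (as discussed below) will be limited to TEAEs, but data listings will include all AEs regardless of their timing". Treatment-emergent means from the first dose to 56 days after the last.

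Two other sources in the SAP would hold the event:

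- SAP 6.3 defines an intercurrent event, "RenalReplace = start renal replacement therapy (dialysis and/or renal transplant"). The sample code in SAP 17.2.2 carries it as the variable ICEDT2.
- SAP 5.5 handles procedures on their own: "Prior and concomitant procedures will be coded using the latest MedDRA version available".

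Neither is linked to graft loss. Section 7.1 of the SAP addendum makes week 52 graft loss descriptive. It extends the rejection list ("one additional preferred term of 'Transplant rejection' is also added based on Apellis team review") and leaves the graft-loss list as it was.

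**The concern.** In someone whose working kidney is a graft, permanent dialysis or a new transplant ordinarily means that the graft has failed. Whether the safety table says so depends on the words the site reported and the term they were coded to. Protocol 4.2 attributes allograft loss in these diseases to disease recurrence, so a site could plausibly report the recurrent disease or renal failure. Protocol 11.2.5 makes severe acute kidney injury an event of special interest, which offers another label for a failing graft.

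The same participant could then be a RenalReplace case in the efficacy analysis and have no graft loss in the safety analysis. Everyone receives pegcetacoplan after week 26, so the week 26 table is the only randomized comparison of graft loss. With few post-transplant participants, each case counts.

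**Working it through.** The documents state no rate, sample size or expected count for graft loss, so there is no figure of the plan's own to reproduce. The check is a reading of the definitions, with a small calculation for scale.

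**1. Routes by which the event can be left out of the count**

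| How the event enters the database | Seen as RenalReplace? | In the graft-loss count? |
|---|---|---|
| AE coded to one of the five terms, inside the TEAE window | Yes, if dialysis or transplant started | Yes |
| AE coded to another term (for example renal failure) | Yes | No |
| Recorded only as a procedure | Yes, if identified as dialysis or transplant | No |
| AE coded to one of the five terms, more than 56 days after last dose | Yes | No |

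The last row needs no miscoding. The randomized period nominally ends on day 182, and 182 − 56 = 126 (week 18). Anyone whose last dose is before day 126 has part of the randomized period outside the TEAE window. Example: last dose at week 12 (day 84), so the window closes on day 84 + 56 = 140. Dialysis at week 22 (day 154) is 154 − 84 = 70 days after the last dose: outside the window, inside the period. Protocol 7.3.1 encourages such participants to complete the remaining visits, so the event can be observed.

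**2. Size of one missed case**

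Inputs: at most 22 post-transplant participants planned (Protocol 6.2, SAP 3.1) and 1:1 allocation (SAP 3.2). Assumption: the cap is reached and splits evenly, 22 / 2 = 11 per arm.

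Shift in one arm's incidence = 1 / n:

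- n = 11: 1/11 = 9.1 points. Exact 95% intervals: 0/11 gives 0% to 28%; 1/11 gives 0.2% to 41%.
- n = 5 (assumed low enrolment): 1/5 = 20 points.
- n = 23 (outer bound): the protocol's summary of changes reports 124 enrolled. With the minimum of 78 native-kidney participants, at most 124 − 78 = 46 could be post-transplant, and 46 / 2 = 23. Then 1/23 = 4.3 points.

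**3. Effect on the test, at 11 per arm**

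Two-sided Fisher p: 0 v 1, 1.0; 0 v 2, 0.476; 0 v 3, 0.214; 0 v 4, 0.090; 0 v 5, 0.035. One case changes the tabulated incidence, but crosses 0.05 only in the step from 4 to 5 against none.

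**The case against.** The strongest reply is that an omission needs two things: a transplant recipient must start permanent dialysis or be re-transplanted, and no qualifying treatment-emergent term may be recorded. Nothing in the documents shows how sites report graft failure, and the five terms cover its obvious names. Entry requires an eGFR of at least 30 and limits scarring on any baseline biopsy, and the randomized period is 26 weeks, so there may be no such case. This stands: the point is that the event may be missed, not that it will be.

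A reader might infer that the plan loses these events or makes the effect on grafts impossible to read. The documents do not support that. TEAEs and serious TEAEs are tabulated by term, events of special interest have their own tables, and procedures are summarized by arm (SAP 5.5 and 7.1). SAP 6.4.1 reports the reasons for monotone missing uPCR data. What may be wrong is the graft-loss count itself.

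A reader might also infer that any difference between RenalReplace and graft-loss counts is a contradiction. It is not: RenalReplace does not separate temporary from permanent dialysis, and temporary dialysis need not mean that the graft is lost.

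Two further limits stand. The term list sits under the overall TEAE summary, so its application to the week 26 table is an inference, although no other definition is offered. And the table would be sparse in any case: at 0 v 1 the p-value is 1.0 and the intervals overlap almost wholly.

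The reply does not answer the structural point. The SAP flags the event for efficacy and does not use it for the safety endpoint that it bears on. Nor does it answer the 56-day gap, which applies even to a correctly coded event.

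**Conclusion.** The concern holds as a risk of undercounting. As written, SAP 7.1 can leave a graft loss out of the endpoint because of coding, recording or timing, while the efficacy analysis treats the same participant as having started renal replacement therapy. The result would be a safety count that is too low and inconsistent with the efficacy data, although the underlying records stay visible.

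At an assumed 11 per arm, one missed case is worth about 9 points of incidence in that arm. The range is about 4 points at the outer enrolment bound to 20 points at 5 per arm. The documents give neither actual post-transplant enrolment nor the number affected, which may be zero.

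No primary, key secondary or multiplicity-controlled result is touched. This is a cheap improvement, not a threat to the trial's conclusions. The addendum's late addition to the rejection list, in a version dated 10 February 2025 after the primary study report of 05 December 2024, shows that a list of this kind can need extending. It does not show that the graft-loss list missed anyone.

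**What to change.** In SAP 7.1, define graft loss in post-transplant participants as the earliest of:

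- (a) an event coded to one of the five listed preferred terms;
- (b) a RenalReplace event that review before database lock, blinded to arm, confirms as re-transplantation or as permanent rather than temporary dialysis;
- (c) removal of the graft in the procedure data.

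Apply this whether or not the event falls in the TEAE window. Count each participant once, state that the definition governs the week 26 tabulation, and use the same rule at week 52. If the outputs are already final, report the reconciled count as a labelled supplementary table beside the existing one.

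The cost is SAP wording, a link to intercurrent-event and procedure data already collected, and a blinded review of the few dialysis cases. It is slightly more than a merge, because the documents do not define permanent dialysis. The clinical team would have to write that criterion down before the review. Part (c) overlaps one listed term but catches a removal recorded only as a procedure.

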1. INTRODUCTION

This statistical analysis plan (SAP) provides a technical and detailed elaboration of the statistical analyses of efficacy, safety, and pharmacokinetic/pharmacodynamic/immunogenicity data as described in the study protocol Amendment 4 dated 25 April 2024. Specifications for tables, figures, and listings are contained in a separate document.

The current SAP describes analysis of the randomized controlled period (RCP, up to week 26). Analysis on the interim data post-week 26 at the time of the datacut, referred to as the open-label period (OLP) reporting, will be provided in an SAP addendum.

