3.5. Analysis Timing and Unblinding

The analysis of data from the RCP of the study will be performed when all participants have completed the RCP or discontinued early and all corresponding data have been entered into the database, reviewed, cleaned, and finalized, and the week 26 Analysis database locked. At that time, the sponsor analysis team will be unblinded to the treatment code, and the primary analysis will be performed, which will include all efficacy and safety analyses for the RCP.

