13.3. Definition of Baseline, RCP, and OLP

For all evaluations unless otherwise noted, baseline is defined as the most recent non-missing measurement prior to the first administration of study drug. Baseline can be the same date as first dose, given the measurement is expected prior to first dose when only date information is available.

In by-visit summary tables, the baseline will be summarized using all available data, but also for each visit using only the baseline data from participants with available data at the visit; hence the mean change from baseline will equal the mean visit value – mean baseline value.

Throughout this document 'change from baseline' refers to the actual change from baseline (ie, visit value – baseline value).

The date when a participant receives first administration of OLP drug will be defined as the start date of the participant's OLP, and that date minus one day will be the end date of the participant's RCP.

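### The exposure-adjusted AE rate formula lets person-time run past the first open-label dose, so RCP rates are wrong for participants who enter the open-label period; the impact is low and the fix is cheap

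*SAP*

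**What the plan says.** Section 7.1 of the main SAP plans two exposure-adjusted summaries, one for all treatment-emergent adverse events (TEAEs) and one for serious TEAEs. It describes the denominator as "the total duration of exposure of the participants at risk during treatment". The formula is 100 times the number of participants affected, divided by exposure-years. A participant with the event contributes time to first onset. For a participant without it, "time to onset is censored as follows: time to onset of the event = (last dose date + 56 days" after the last dose, less the Day 1 date plus 1. No alternative stopping date is given, and last dose is not tied to a study period.

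The same section defines TEAEs as running "up to 56 days beyond the last dose of investigational product".

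The period limits are stated elsewhere. Section 1: "The current SAP describes analysis of the randomized controlled period (RCP, up to week 26"). Section 3.5 says that, at the week 26 lock, "the primary analysis will be performed, which will include all efficacy and safety analyses for the RCP". Section 13.3 takes the date of the first OLP dose and says "that date minus one day will be the end date of the" participant's RCP.

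Section 7.1 of the SAP Addendum says "The classification of AEs in the RCP or OLP will be based on the AE start date", compared with the threshold in main SAP Section 13.3. It also says "The same summaries for RCP as in the main SAP will be repeated for OLP".

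Under Protocol Section 6.1.3, both arms move to open-label pegcetacoplan after the RCP. Open-label dosing starts at the first visit after the week 26 biopsy, or at week 26 for adolescents without a biopsy.

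**The concern.** A person-time rate is interpretable only if numerator and denominator cover the same window. For someone who goes straight from blinded to open-label dosing, the RCP closes the day before the first OLP dose, yet the formula credits event-free time to 56 days after the last dose. If last dose means the last blinded dose, those extra days lie in the OLP. In the placebo arm they are days on active drug counted as placebo exposure.

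The 56 days suit a participant who stops treatment and is followed, because they match the TEAE window. They do not suit a participant who changes period. What is at stake is the absolute rate per 100 person-years, for serious TEAEs as well as all TEAEs, which is the quantity these two tables exist to provide.

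**Working it through.** The documents state no exposure-adjusted rate, so there is no planned figure to reproduce. The check applies the SAP formula to the protocol timetable.

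**Inputs**
- Study days (Protocol Table 2): week 26 is day 182 and week 28 is day 196.
- RCP end, T (SAP 13.3): day 195 for a week 28 OLP start, day 181 for a week 26 start.
- Counted event-free time, C = last blinded dose day + 56 (SAP 7.1).
- Last blinded dose day (assumed; dosing is twice weekly): 182 to 193 for a week 28 start, giving C = 238 to 249; 178 to 181 for a week 26 start, giving C = 234 to 237.
- Excess days, C − T: 43 to 54 (week 28 start) and 53 to 56 (week 26 start). All of them fall in the OLP.
- Participants: 124 enrolled (protocol summary of changes), 1:1, so 62 per arm.
- Assumptions: constant hazard, all participants enter the OLP, and p = share with the event during the RCP.

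**Reading A: adverse events assigned to the RCP by start date**

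Hazard h = −ln(1−p)/T. Mean onset among those with the event m = 1/h − T(1−p)/p. Understatement = 1 − [pm + (1−p)T] / [pm + (1−p)C].

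| p | T=195, C=238 | T=195, C=249 | T=181, C=234 | T=181, C=237 |
|---|---|---|---|---|
| 2% | 17.9% | 21.5% | 22.5% | 23.4% |
| 10% | 17.3% | 20.8% | 21.7% | 22.7% |
| 50% | 13.3% | 16.1% | 16.9% | 17.7% |
| 80% | 8.1% | 10.0% | 10.5% | 11.1% |

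As p falls to zero, the understatement tends to (C − T)/C: 43/238 = 18.1%, 54/249 = 21.7%, 53/234 = 22.6%, 56/237 = 23.6%.

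Worked example: week 28 start, 62 per arm, p = 10%.
- Affected: 6.2. Event-free: 55.8.
- m = 195/0.10536 − 195 × 0.9/0.1 = 1850.8 − 1755 = 95.8 days.
- Person-years stopped at RCP end: (6.2 × 95.8 + 55.8 × 195)/365.25 = 31.4. Rate: 620/31.4 = 19.7 per 100.
- Person-years as written: 38.0 (C = 238) or 39.7 (C = 249). Rate: 16.3 or 15.6 per 100.

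If only a share f enters the OLP and the rest have no mismatch, the 17 to 21% in this example becomes 16 to 19% at f = 0.9 and 14 to 17% at f = 0.8.

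Between-arm ratio, week 28 start, both arms affected alike: a true ratio of 2.0 becomes 2.00 at 2% control incidence, 2.02 at 10%, and 2.09 to 2.11 at 50%.

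**Reading B: TEAEs counted over the full window to last dose + 56 days**

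Numerator and denominator now match, but the last 43 to 56 days of each event-free entrant's time, 18 to 24% of it, are open-label. Events in those days enter the RCP rate. For placebo participants they are events on pegcetacoplan. The size cannot be computed without event rates.

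**The case against.** The best reply is that Section 7.1 is consistent within itself. The TEAE window and the censoring rule both end 56 days after the last dose, and no sentence in that section closes the numerator at the first OLP dose. The explicit start-date rule is in the Addendum, for a display whose only RCP column is pegcetacoplan. For the main SAP tables, closure is inferred from Sections 1, 3.5 and 13.3. This stands against one tempting reading, that the plan as written certainly makes RCP rates too low. The documents support that direction only under Reading A. It does not rescue the rule, because Reading B puts open-label events and time into tables meant for the RCP.

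Second, the phrase about being at risk during treatment, read strictly, would also exclude the 56 days for participants who discontinue. That is fair, so the point rests on the period definitions and not on that phrase.

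Third, Section 1 leaves table specifications to a separate document. That would answer silence, but here the SAP gives an explicit formula. Its own time-to-event analyses (Section 6.7.5) use a minimum rule involving last contact, treatment discontinuation and week 26.

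Fourth, the missing stops at death and last contact have no demonstrated effect. Protocol Section 7.3.1 encourages participants who discontinue to complete the RCP visits, and asks those stopping after week 18 to have an exit visit about 8 weeks after the last dose. No magnitude is claimed for these two stops.

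**Conclusion.** The formula is wrong as written for participants who enter the OLP, with low impact. Under start-date assignment, absolute exposure-adjusted RCP rates are understated by roughly 17 to 23% at 2 to 10% incidence and 8 to 11% at 80%. These figures are illustrative. They rest on a constant hazard, last dose meaning last blinded dose, and universal OLP entry, and the documents give no adverse event rates. Under the literal 56-day window the error is contamination by open-label events and time, with no stated direction.

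A reader might infer that the comparison between arms is distorted or that the trial's safety conclusions are at risk. The documents do not support that. Two descriptive tables are affected, the between-arm ratio barely moves when both arms enter the OLP alike, crude incidence tables do not use this person-time, and no formal test or endpoint depends on it. The Addendum does not state the start and censoring dates of the adverse event clock for each of its columns, but that is a matter for clarification and not an error.

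**What to change.** In SAP Section 7.1, define last dose as the last dose in the period being reported. Censor event-free participants at the earliest of that dose plus 56 days, the day before the first OLP dose (RCP columns), death, last contact and data cut. Count RCP TEAEs over the same window. Keep the 56 days for participants who discontinue and are followed. The death and last-contact stops are tidying.

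As a clarification, add one sentence per column to the Addendum giving the start date, last dose and censoring date of the clock.

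The cost is one derived date and a few sentences, using dates already needed for the study. If events have been assigned by start date, absolute RCP rates will rise. Crude incidence tables will not change if they already assign events to the RCP by start date.
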